Recent studies showed that alternative therapies are used as first aid treatment for burns as Aloe Vera, saliva and a tea tree oil impregnated dressing applied as first aid to a porcine deep dermal contact burn, results of it showed significantly decrease sub dermal temperature within the skin during the treatment period.

Tea tree oil [TTO] (*Melaleuca alternifolia*) is a clear, colorless to pale yellow liquid, and is insoluble in water. It is lipophilic and works through penetrating the skin and mucous membranes. The active ingredients responsible for killing bacteria and fungi in TTO include terpinene-4-ol, alpha-terpineol and alphaphinene, which inhibit cell respiration and disruption of cell membrane permeability with the resultant leakage of potassium.

Inherent in the previous statements, is the belief that there is a need to investigate whether TTO would be more cost effective, enhance rapid healing than the conventional topical agent.

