### **Aim of the study**

Compare the effect of two topical dressing techniques on the healing of second degree burn wounds; *melaleuca alternifolia* (tea tree oil) and conventional dressings.

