**Patient's inclusion criteria will include:**

- Adults of both genders (18-60 years), able and willing to cooperate and communicate.
- Newly admitted to the study setting with recent 2nd degree burns whether superficial or deep ≤10%TSBA.
- Free of associated illness that affect wound healing as DM, immune disorder, or associated injuries.
- Free from pre-existing skin conditions such as eczema

**Tools:** Two tools will be used on this study:

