**Tool I: (Burn patient's assessment sheet)**

This tool will mainly aim to assess burn parameters (as extent, depth, and cause of burn), criteria of wound healing (as wound color, appearance of burn wound, signs of infection and presence of exudates). It will be comprised of three parts.

**Part I: Patient Sociodemographic data:** including:

- Personal characteristics: as Patients' age, gender, level of education, occupation, date of burn, date of admission, date of discharge and habits.
- Patient history including past and present history.

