**Part II: Laboratory studies:**

- Complete blood count.
- Serum proteins.
- Electrolytes.

**Part III: Burn parameters:** This part will include data regarding: Site of burn, extent, cause, and depth.

**Part IV: Type of wound dressing:** Whether TTO or Conventional dressing.

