**-Morphological changes of the wound:**

This part will be used to assess burn wound healing, and determine signs of infection including signs of inflammation as wound color, presence of exudates (amount, color, and type), size, depth, edema, as well as frequency of dressing change.

- **Photographic pictures:**

Colored digital photographs will be taken three times to assess wound healing process (day of burn, each other day till healing and after one month)

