## **Method**

1. Written approval will be obtained from the hospital administrator and head of Burn Department, after explanation of the study aim.
2. The study tools will be developed by the researcher after review of relevant literature.
3. The developed tools will be submitted to 5 experts in the fields of plastic surgery &burn and Medical Surgical Nursing to test its content validity and necessary modification will be done accordingly.
4. Reliability of the tool will be tested.
5. Ethical considerations:
  - a. Patient's written informed consent will be obtained after explanation of the study aim.
  - b. Confidentiality, privacy and right of withdrawal will be assured.
  - c. Ethical committee approval will be obtained.
6. Pilot study will be conducted on 5 patients for testing, clarity, feasibility and applicability of the developed tools and modification will be done.
7. The study subjects meeting inclusion criteria and will be sequentially divided into two groups, the first group will receive conventional dressing (control group), and this dressing will be changed routinely once every other day. For the second group the wound will be dressed by TTO, which will be changed every other day till healing occurs. This frequency is advocated, since more frequent dressing change will interfere with granulation tissue formation.
8. All burn wound will be washed gently with Saline, and all open blister and loose non-viable tissue will be removed from the burn, intact blisters will be

left, and then the topical agents will be applied directly on wound. Burns involving body joints will be kept in functional position.

9. Initial assessment of all patients will be done using tool I. Subsequent assessment will be done on 4th, 14th, 21th of topical dressing agents use until the wound healing from both groups using tool II.
10. Colored digital photographs will be taken-if possible- to assess wound healing process at the (day of burn, each other day till healing, after one month)
11. Initial and ongoing assessment results for the conventional dressing, compared to TTO dressings, will be carried out using appropriate statistical methods.

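### If speed of healing is to be compared, record healed yes/no at each planned dressing change: the dated sheets alone place healing only within about 4, 10 or 7 days

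*Combined protocol and SAP*

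**What the plan says.** The Aim is to "Compare the effect of two topical dressing techniques on the healing of second degree burn wounds". The Introduction adds the question of whether TTO would "enhance rapid healing than the conventional topical agent". No section names time to healing as an endpoint; Method item 11 compares the initial and ongoing assessments.

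Five places bear on when healing is observed:

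- **Method item 9** dates Tool II at the 4th, 14th and 21st "of topical dressing agents use until the wound healing from both groups using tool II". The unit is not printed; days are assumed here.
- **Method item 7** has dressings changed every other day in both groups. Only the TTO sentence adds that this continues to healing.
- **Tool II, morphological part** lists wound items including "presence of exudates (amount, color, and type), size, depth, edema, as well as frequency of dressing change". It lists no healing date.
- **Tool II, photographs** are scheduled for "day of burn, each other day till healing and after one month", under a stated count of three and without a condition. Method item 10 repeats the schedule but makes it conditional on feasibility.
- **Tool I, Part I** lists "date of burn, date of admission, date of discharge and habits" among the personal data, again without a healing date.

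The Statistical Analysis Plan offers a t-test or Mann-Whitney test for quantitative variables and prints a 0.5% significance level. It names no time-to-event method.

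**The concern.** A question about rapid healing is answered most directly by the day each wound healed. On healed status alone, the dated sheets cannot separate a wound that healed on day 5 from one that healed on day 14: both are unhealed on the first sheet and healed on the second. A difference of several days that falls between two sheets could be missed in a study with 25 patients per group. A healing day not written down during care may not be recoverable later.

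The planned t-test or Mann-Whitney test could compare healing days only if every patient were followed to healing. A discharge date is recorded, so some patients may leave unhealed, and the plan has no rule for them.

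**Working it through.** The plan gives no healing time, standard deviation (SD), effect size or power, so it has no figure of its own to reproduce.

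**1. Width of the interval that contains healing.** The inputs are the sheet dates in item 9 and the dressing interval in item 7.

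| Record | Arithmetic | Width |
|---|---|---|
| Start to first sheet | 4 − 0 | 4 days (4 − 1 = 3 if use starts on day 1) |
| First to second sheet | 14 − 4 | 10 days |
| Second to third sheet | 21 − 14 | 7 days |
| After third sheet | no further date | open |
| Each planned dressing change | every other day | about 2 days |

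**2. What this could mean for power (illustration only).** Every healing-time input is assumed. Each scenario has 25 patients per group and a two-sided 5% level. Healing is normally distributed in the control group, with mean 13 days and SD 3 for superficial burns, and mean 21 days and SD 4 for deep burns. The 2-day record rounds the healing day up to the next even day. The comparator reduces the sheets to four healed-status categories (by day 4, by 14, by 21, later). The test is the log-rank stratified by depth.

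| Benefit | Share deep | 2-day record | Sheet categories | Difference (points) |
|---|---|---|---|---|
| 4 days | 30% | 97.6% | 86.6% | 11.0 |
| 4 days | 50% | 96.2% | 85.1% | 11.1 |
| 4 days | 70% | 93.9% | 84.6% | 9.3 |
| 3 days | 30% | 84.6% | 66.1% | 18.5 |
| 3 days | 50% | 79.5% | 63.0% | 16.5 |
| 3 days | 70% | 75.2% | 62.1% | 13.1 |

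The gain is about 9 to 18 points in these six cases.

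**3. Why stratify.** Both depths are eligible ("degree burns whether superficial or deep"), and they are assumed here to heal at different speeds. At 30% deep with a 4-day benefit, the unstratified log-rank on the 2-day record has 69.3% power, against 97.6% when stratified.

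**4. Patients who leave.** If 20% are assigned to leave at a random day from 4 to 20, unrelated to healing, the stratified 2-day power becomes 96.4/94.3/90.7% for a 4-day benefit and 81.5/75.3/70.0% for a 3-day benefit.

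**5. The printed level.** In a single-depth Mann-Whitney example (means 12 and 9 days, SD 3), power is 91% with 2-day recording and 63% with sheet dates at 5%. At 0.5% these fall to 66% and 21%.

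**The case against.** **No healing-speed endpoint is planned.** This stands. Speed appears only in the rationale, and a comparison of wound state on fixed days needs no healing day. A reader might infer that the plan fails to measure its own endpoint. The documents do not support that, and the point applies only if speed is compared.

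**Healing is already observed every other day.** This stands in part. Photographs belong to Tool II, staff uncover wounds at each change, and the listed frequency of dressing change, if it means a count, would give an approximate healing time. What is missing is a rule that turns any of these into a dated healing record in both groups. The tools are still to be developed, reviewed and piloted, so the field can still be added.

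**The categories discard what the sheets record.** This also stands. Tool II lists wound size and exudate, so wounds healing on days 5 and 14 might already differ on the day-4 sheet. With control mean 10 days, SD 3, a 3-day benefit and assumed linear shrinkage, a Mann-Whitney test on day-4 size has 90, 82 or 62% power for size error SD of 5, 10 or 20%, against 56% for the categories. The gains in the table are therefore not the loss of the plan as written.

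**A much larger loss might be inferred.** If all deep burns have a control mean of 28 days, the categories give about 53% power against 92%, a gap of 39 points. That gap comes mainly from pooling all healing after day 21. Item 9 can be read as continuing to healing, and a one-month photograph is listed. One further cut at day 30 reduces the gap to about 12 points.

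**Items 7 and 9 might be read as conflicting.** They do not: one sets dressing changes, the other sets assessments.

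**Conclusion.** The point holds as a worthwhile, inexpensive improvement and not as an error. If speed of healing is compared, the only unconditional dated follow-up sheets place healing within about 4, 10 or 7 days, then leave it open; recording at each planned change would give about 2 days. This rests on reading the sheet dates as days from first use of the topical agent, and on healed status alone.

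The precision gain follows from the schedule. The power gain of about 9 to 18 points does not: it depends on assumed healing times and depth mix, on a 5% level, and on a comparator that ignores wound size and photographs. It is smaller where those are usable, and the powers themselves are lower at the printed 0.5% level. The gain is neither a bound nor an estimate for this trial.

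**What to change.** **Method item 9.** Add that at every planned dressing change, in both groups, healed yes/no and the date are recorded on Tool II. Use one outcome definition of healed built from Tool II items (for example size and exudate), identical in both groups, put to the five experts of item 3, and used for outcome recording only. Healing day is counted from the first application of the assigned topical agent to the first change recorded as healed.

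**Dressings that end early.** If dressings end before the definition is recorded as met, record healed status at that last change and at any later planned Tool II sheet or photograph. Report the number of such patients per group.

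**Statistical Analysis Plan.** Add a comparison of healing day by a log-rank test stratified by burn depth, which Tool I, Part III already records ("Site of burn, extent, cause, and depth"). Patients unhealed at last observation are censored on that day and counted per group.

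**Photographs.** Reconcile Tool II with Method item 10 on how many are taken and whether they are conditional. Where taken, use them to check the recorded day.

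No change to the dressing interval or to when treatment stops is proposed.

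**Cost.** No visits are added while dressings continue. Data entry is about 10 lines per patient to day 21 (21 ÷ 2, rounded down) and 14 to day 28 (28 ÷ 2). Over 50 patients this is about 240 to 675 lines, depending on the healing times assumed. One definition joins an expert review already planned. The main weakness is follow-up after discharge, because no section says who sees dressing changes then. Censoring is valid only if leaving, or ending dressings, is unrelated to healing.

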#### **Statistical Analysis Plan (SAP):**

Data will be analyzed using IBM SPSS software package version 23.0. The Shapiro-Wilk will be used to verify the normality of distribution of variables; Comparisons between groups for categorical variables will be assessed using Chi-square test (Monte Carlo or Fisher Exact). Student t-test will be used to compare two groups for normally distributed quantitative variables, Mann Whitney test will be used to compare two groups for not normally distributed quantitative variables, Friedman Test for multiple comparisons between the different periods in each group. Significance of the obtained results will be judged at the 0.5% level.

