### **Materials and method**

#### **Materials**

**Design:** An experimental design will be utilized.

**Setting:** The present study will be conducted at the burn unit, Alexandria Main University Hospital, Alexandria, Egypt.

**Subject:** A convenient sample of 50 patients admitted to burn unit suffering from second-degree burns will be included in the present study.

The fifty patients will be sequentially enrolled into two equal groups:-

- The first group (25 patients) will be managed conventional dressings (control group).

- The second group (25 patients) will be managed by local application tea tree oil (study group).

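### The SAP gives ordered wound grades no between-group test that uses their order; any Tool II item with three or more grades would go to chi-square and lose power at 25 per arm

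*Combined protocol and SAP*

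**What the plan says.** The Statistical Analysis Plan section sets the between-group rule by type of variable. For categorical variables: "Comparisons between groups for categorical variables will be assessed using Chi-square test (Monte Carlo or Fisher Exact"). For quantitative variables that fail the normality check: "Mann Whitney test will be used to compare two groups for not normally distributed quantitative variables". The section names no trend test, proportional-odds model or other ordinal method for comparing the two dressings. For change over time within a group it lists the "Friedman Test for multiple comparisons between the different periods in each group", which ranks the data, but it does not say which variables this covers.

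Tool II, under morphological changes of the wound, records among other things "presence of exudates (amount, color, and type), size, depth, edema". It gives no levels, scores or units, and does not say which items are categorical. The only depth classes in the protocol are in the inclusion criteria: "degree burns whether superficial or deep". The Method section says the tools are still to be developed, reviewed by experts, tested for reliability and piloted.

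Each arm has 25 patients (Materials). No effect size, power or primary outcome is stated.

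**The concern.** A chi-square test on a table with three or more ordered columns ignores their order. A move from heavy to no exudate counts no differently from a move between any other two labels, and the test spreads its sensitivity over every possible pattern of difference (K − 1 degrees of freedom for K grades). The study's question has a direction: does the wound do better under one dressing? A rank or trend test puts one degree of freedom on that question.

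With 50 patients and no planned increase, a consistent shift towards better grades is more likely to be missed under the stated rule than under a test the SAP already names for other data. The rule also attaches no effect estimate to such items.

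**Working it through.** The documents give no power figure to reproduce. The check asks how much power chi-square gives up against a rank test on ordered grades at this sample size.

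**Inputs from the documents.** 25 per arm (Materials: "The first group (25 patients) will be managed conventional dressings (control group") and "The second group (25 patients) will be managed by local application tea tree oil (study group")). Significance level: "Significance of the obtained results will be judged at the 0.5% level". The 5% level is shown as well, in case 0.5% is a slip.

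**Assumptions, not in the documents.** Two-sided tests; K = 2, 3, 4 or 5 grades, equally likely in the control arm; a proportional-odds shift with common odds ratio (OR) 2, 3 or 4.

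**Step 1: the shifted distribution.** If c is the control cumulative probability at a cut, the other arm has odds OR × c/(1 − c). For four even grades and OR 3:
- c = 0.25, 0.50, 0.75, so the odds are 1/3, 1, 3
- multiplied by 3: 1, 3, 9
- cumulative probabilities 0.50, 0.75, 0.90
- grade probabilities 0.50, 0.25, 0.15, 0.10, against 0.25 each in the control arm

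**Step 2: approximate power of chi-square.** The non-centrality is λ = n Σ (p − q)²/(p + q), with n = 25:
- 0.0625/0.75 + 0 + 0.01/0.40 + 0.0225/0.35 = 0.0833 + 0.0250 + 0.0643 = 0.1726
- λ = 25 × 0.1726 = 4.32 on 3 degrees of freedom
- critical values 7.81 (5%) and 12.84 (0.5%) give power of about 38% and 13%

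**Step 3: approximate power of Mann-Whitney.**
- θ, the probability that a patient in the shifted arm has the better grade, ties counted half: 0.50×0.75 + 0.25×0.50 + 0.15×0.25 + ½×0.25 = 0.6625
- expected grade totals T = 18.75, 12.5, 10, 8.75
- tie-corrected variance (n²/12)[(N + 1) − Σ(T³ − T)/(N(N − 1))], N = 50: 52.08 × (51 − 4.149) = 2440, square root 49.4
- expected z = 625 × 0.1625/49.4 = 2.06
- power Φ(2.06 − 1.96) ≈ 54% at 5%, and Φ(2.06 − 2.81) ≈ 23% at 0.5%

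**Step 4: simulation.** 20,000 trials per row, Pearson chi-square against tie-corrected Mann-Whitney. Power in %:

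| Grades | OR | 5%: chi-square | 5%: rank | Loss | 0.5%: chi-square | 0.5%: rank | Loss |
|---|---|---|---|---|---|---|---|
| 2 | 3 | 47.8 | 47.8 | 0 | 16.6 | 15.9 | none |
| 3 | 2 | 19.7 | 25.4 | 5.7 | 3.8 | 6.1 | 2.3 |
| 3 | 3 | 42.8 | 53.1 | 10.3 | 13.7 | 20.6 | 6.9 |
| 3 | 4 | 61.3 | 71.5 | 10.2 | 25.6 | 36.6 | 11.0 |
| 4 | 2 | 17.1 | 26.3 | 9.2 | 2.8 | 6.2 | 3.4 |
| 4 | 3 | 38.7 | 55.8 | 17.1 | 10.7 | 22.2 | 11.5 |
| 4 | 4 | 56.1 | 74.0 | 17.9 | 21.1 | 39.3 | 18.2 |
| 5 | 2 | 14.9 | 27.4 | 12.5 | 2.0 | 6.3 | 4.3 |
| 5 | 3 | 34.3 | 56.5 | 22.2 | 8.2 | 22.8 | 14.6 |
| 5 | 4 | 52.2 | 76.2 | 24.0 | 17.6 | 41.7 | 24.1 |

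The row for four grades and OR 3 agrees with steps 2 and 3 to within about 2 points. A skewed control distribution (10/20/30/40%) gives almost the same losses as four even grades: 9.7, 17.0 and 17.7 points at 5%.

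**Step 5: is the gain bought with false positives?** No. With OR 1 and three to five even grades, both tests reject in 4.7% to 5.1% of trials at the 5% level and in 0.3% to 0.5% at the 0.5% level.

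**Step 6: does the SAP's exact option recover the order?** No. With Monte Carlo exact p-values for both tests (1,000 trials), four grades and OR 4 give 57% against 73% at 5%, and 23% against 40% at 0.5%.

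**Step 7: where the rank test is worse.** If the arms differ without a consistent direction, the result reverses. For 20/60/20% against 45/10/45%, chi-square has 95% power at 5% and the rank test 7%. For 40/30/20/10% against 40/5/45/10% the figures are 61% and 13%.

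**The case against.** The strongest reply is that the documents never say these items are graded. A reader might infer from the Tool II list that exudate amount, oedema and depth are all ordered scales, and that all three are being mishandled. The text does not support that. Depth appears only as superficial or deep, where the choice of test makes no difference. Oedema could be present or absent. Exudate amount could even be measured. This part of the objection stands, and it makes the point conditional.

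It can also be said that scored items might go to Mann-Whitney in practice, and that listing Friedman suggests ranked or numeric data are expected. That is possible, but the SAP assigns no item to a test. On its plain wording a grade is categorical and goes to chi-square. The same item could then be ranked within groups over time and treated as unordered between groups, although the comparison between dressings is the study's aim.

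A reader might also take the power losses as a property of this trial. They are not: the number of grades, their distribution and the odds ratios are all assumed. Nor is the cost of switching always slight, as step 7 shows; those examples are extreme, but they rule out a claim that the rank test is better in every case.

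Finally, chi-square does not hide the direction of an effect, because the protocol's Results section says the data will be tabulated. What is missing is an effect estimate, and a bare Mann-Whitney p-value would lack one too.

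**Conclusion.** The concern holds in conditional form. As worded, the SAP compares any Tool II item with three or more ordered grades by a test that ignores the order. Exudate amount is the likeliest such item; oedema qualifies only if it is graded. Under the assumptions listed (25 per arm, three to five even grades, proportional-odds shift, OR 2 to 4, two-sided), the loss is about 6 to 24 percentage points at 5% and about 2 to 24 points at the stated 0.5%. For two-level items it is nil.

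The 0.5% level is a separate matter and cuts power at least as much: for four grades and OR 3, chi-square falls from 39% at 5% to 11% at 0.5%. Changing the test does not cure that.

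This should be corrected, because the rule is explicit and a better one is readily available. It does not by itself undermine the trial.

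**What to change.** In the Statistical Analysis Plan section, add:

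> Any Tool II item recorded in three or more ordered grades (e.g. exudate amount) will be compared between groups with the Mann-Whitney or linear-by-linear test (exact or Monte Carlo), with a common odds ratio and 95% CI; chi-square/Fisher is kept for binary and unordered items (exudate colour and type, cause, site). The full table of grades will be shown by arm.

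Choose one of the two ordinal tests before the data are seen. In Tool II, list the levels of each item; the planned expert review and pilot are the natural point to settle them.

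The cost is one or two sentences in the SAP and a list of levels, with no new patients or measurements. The downside is that an ordinal test can miss a non-monotone difference that chi-square would detect, which is why the full grade table should be reported.

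### The SAP chooses Student's t-test on normality alone; if numbers and spreads both differ between arms at later visits, its error rate can drift either way, and naming Welch's test is a nearly free safeguard (minor)

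*Combined protocol and SAP*

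**What the plan says.** The section Statistical Analysis Plan (SAP) is one paragraph. The check it names is "The Shapiro-Wilk will be used to verify the normality of distribution of variables". Two branches follow for quantitative variables: "Student t-test will be used to compare two groups for normally distributed quantitative variables", and otherwise "Mann Whitney test will be used to compare two groups for not normally distributed quantitative variables". It mentions no check of equal variances, no unequal-variance version of the t-test and no expected SD. On the error rate it says "Significance of the obtained results will be judged at the 0.5% level", without stating sidedness.

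Under Materials the sample is "A convenient sample of 50 patients admitted to burn unit suffering from second-degree burns", and "The fifty patients will be sequentially enrolled into two equal groups", that is, 25 per group.

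Method, item 9, schedules follow-up on the 4th, 14th and 21st day "of topical dressing agents use until the wound healing from both groups using tool II". Item 11 says that initial and ongoing results will be compared between the dressings. The morphological part of Tool II records "presence of exudates (amount, color, and type), size, depth, edema, as well as frequency of dressing change" together with wound color. Wound size is the clearest candidate there for a quantitative variable.

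**The concern.** Student's t-test rests on two distributional assumptions, normality and equal variances. The SAP checks the first and leaves the second open. With equal arms the second hardly matters. With unequal arms, the pooled standard error gives too much weight to the variance of the larger arm. If the smaller arm is the more variable, the standard error is too small and the test rejects too often. If the larger arm is the more variable, the test rejects too rarely and loses power.

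The arms start equal. However, if assessment stops at healing, fewer patients are measured on days 14 and 21, and the numbers may fall unequally. Spreads may differ as well: superficial and deep second-degree burns are both eligible (inclusion criteria), and the groups are formed sequentially from a convenience sample with no randomisation described. Case mix could therefore differ between arms even without any dressing effect. What is at stake is the stated error rate of between-dressing comparisons at the later visits.

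**Working it through.** **The plan's own figure.** The sample of 50 cannot be reproduced, because no effect size, SD or power is given. The only stated error rate is the significance level. It is written as 0.5%, possibly a slip for 5%, which needs confirming separately. Both levels are shown, two-sided by assumption.

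**Inputs.** From the documents: Student's t-test, and 25 per arm at the start. Assumed, because the documents are silent: the numbers measured at later visits, the SD ratio, and normal data.

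**Why both conditions are needed.** With arm sizes n1, n2 and SDs s1, s2:

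- True variance of the mean difference: s1²/n1 + s2²/n2.
- Variance that Student's test estimates on average: [((n1−1)s1² + (n2−1)s2²)/(n1+n2−2)] × (1/n1 + 1/n2).

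Taking SDs of 1 and 1.5:

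- 25 v 25: true (1 + 2.25)/25 = 0.130; pooled [(1 + 2.25)/2] × 0.08 = 0.130. They agree.
- 20 v 10, smaller arm more variable: true 1/20 + 2.25/10 = 0.275; pooled [(19×1 + 9×2.25)/28] × 0.15 = 0.210. The standard error is too small by a factor √(0.210/0.275) = 0.87.
- 20 v 10, larger arm more variable: true 2.25/20 + 1/10 = 0.2125; pooled [(19×2.25 + 9×1)/28] × 0.15 = 0.277. The standard error is too large by a factor √(0.277/0.2125) = 1.14.

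**Error rates.** Simulation with equal means and normal data, 1,000,000 trials per row. Percent rejected at nominal 5%, with nominal 0.5% in brackets:

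| Arms | SDs | Student | Welch |
|---|---|---|---|
| 25 v 25 | 1, 1 | 5.0 (0.50) | 5.0 (0.49) |
| 25 v 25 | 1, 2 | 5.2 (0.56) | 5.0 (0.50) |
| 25 v 25 | 1, 3 | 5.4 (0.63) | 5.0 (0.51) |
| 20 v 10 | 1, 1 | 5.0 (0.51) | 5.0 (0.55) |
| 25 v 20 | 1, 1.5 | 6.1 (0.74) | 5.0 (0.51) |
| 25 v 20 | 1.5, 1 | 4.2 (0.37) | 5.0 (0.50) |
| 20 v 10 | 1, 1.5 | 8.6 (1.35) | 5.1 (0.58) |
| 20 v 10 | 1.5, 1 | 2.7 (0.18) | 4.9 (0.48) |
| 18 v 8 | 1, 2 | 12.6 (2.73) | 5.2 (0.64) |
| 18 v 8 | 2, 1 | 1.6 (0.08) | 4.9 (0.49) |

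Unequal numbers with equal spreads do no harm, and unequal spreads with equal numbers do little. The error moves materially only when both differ. In relative terms the inflation is larger at 0.5%, the level as written. With only 5 patients in an arm Welch is also off, reaching 0.94% at nominal 0.5% for 15 v 5 with the smaller arm at twice the SD.

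**Cost of Welch when variances are equal.** Power for a difference of 0.8 SD at the 5% level: 79.2% (Student) against 79.1% (Welch) at 25 v 25, and 51.4% against 49.7% at 20 v 10.

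**The case against.** A reader might infer that the test's error rate is wrong at days 14 and 21. The documents do not support that, for these reasons.

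- **The later numbers and spreads are assumed.** The only stated arm size is 25, where Student's test is close to nominal. The 18 v 8 rows with an SD ratio of 2 are severe cases, and nothing in the documents says which arm would be smaller or more variable. This stands.
- **Without a dressing effect and with comparable groups, the problem largely disappears.** Healing and spread then share one distribution, and numbers differ only by chance. A simulation of that situation (25 per arm, about 40 to 70% still unhealed) gave 4.6 to 5.2% for Student's test at nominal 5%, with a gap of 10 or more patients in under 1% of trials. This stands for comparable groups. Sequential allocation with no randomisation described, and a mix of burn depths, do not guarantee comparability.
- **Healed patients may not leave the comparison.** If a healed wound is recorded as size zero, the arms stay at 25 apart from losses. The zeros would probably fail Shapiro-Wilk: with 28% zeros and the rest normal (mean 5, SD 1.5, assumed), it rejected normality in 99% of samples of 25. The SAP's own rule then leads to Mann-Whitney. The protocol does not say which handling applies, so neither reading can be excluded.
- **Few variables are exposed.** Most Tool II items are categorical. The surest candidates for a t-test are baseline age and laboratory values, compared at 25 v 25. This limits the scope.
- **Pooling is not spelled out.** The word does not appear in the SAP, and SPSS prints both rows. That is itself a reason to name the row in advance, since otherwise the choice between two p-values is open once the data are seen.

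**Conclusion.** The point holds in a conditional form and is minor. The SAP selects what is conventionally the equal-variance test without addressing variances. At the planned 25 v 25 the effect is negligible: 5.2% at an SD ratio of 2 and 5.4% at a ratio of 3, against a nominal 5%. If fewer patients are measured later, and both numbers and spreads differ between arms, the test can be liberal or conservative: about 8.6% or 2.7% at nominal 5% under the assumed 20 v 10 and SD ratio 1.5, and 6.1% or 4.2% at 25 v 20 with the same ratio. These figures rest on assumed numbers, assumed SDs and normal data, and the direction cannot be predicted from the documents.

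A reader might also infer that changing the test would make later-visit comparisons sound. It would not: if only unhealed wounds are compared and the arms heal at different rates, the groups compared are selected, and Welch corrects the variance assumption only.

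**What to change.** In the SAP, replace Student's t-test with *Welch's t-test (equal variances not assumed)* for every between-group comparison of a normally distributed quantitative variable, at every visit. SPSS already prints this row in the same output, so the change costs a few words. If variances are equal, the power loss is about 0.1 point at 25 v 25 and 1 to 2 points at 20 v 10.

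As a companion change, state how a healed wound enters the comparisons at days 14 and 21: left out, or kept with a defined value. That sentence settles how many patients are compared at each visit and makes any selection among unhealed wounds visible, which the choice of t-test cannot do.
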